9.4.1.1. Study Monitoring

Table 7: Specification of Sequential Statistical Analyses

Parameter	Population	Hypothesis	Statistical Method	Criterion	Monitoring Plan
Potential Harm ^a of Symptomatic Cases	FAS	$H_0: VE \geq 0\%$ vs. $H_1: VE < 0\%$	Exact 1 sided binomial test of the fraction of infections assigned to who receive the vaccine.	Constant p value cut off controlling α at 5%	After every event starting from the 12 th event ^b
Potential Harm ^a of Severe Cases	FAS	$H_0: VE \geq 0\%$ vs. $H_1: VE < 0\%$	Exact 1 sided binomial test of the fraction of infections assigned to who receive the vaccine.	Unadjusted p value α at 5%	After every event starting from the 5 th event

CI confidence interval; FAS full analysis set; PP per protocol; VE vaccine efficacy.

^a Harm in the form of an increased rate of symptomatic COVID 19 events due to vaccination (which meet the mild, moderate or severe/critical case definition).

^b Monitoring stops when the primary efficacy analysis is triggered.

^c The monitoring can only start as soon as the conditions outlined in Section 9.4.1 are met.

The boundary of potential harm will be monitored by an SSG. Once a boundary has been crossed, the SSG will inform the IDMC and an IDMC meeting will be organized. The statistical details of the decision rules and the frequency of evaluation and operational implementation will be fully detailed in the SAP and IDMC Charter.

9.4.2. Secondary Endpoints for the Double-blind Phase

All secondary endpoint analyses for the double-blind phase will occur in the PP analysis set, in seronegative participants unless otherwise indicated.

To evaluate the effect of the vaccine against symptomatic molecularly confirmed COVID-19, including mild infections, a BOD endpoint will be evaluated based on the first occurrence of molecularly confirmed COVID-19, including mild, moderate and severe/critical case definitions in Sections 8.1.3.1 and 8.1.3.2, with onset at least 14 days after the second vaccination (Day 71) with Ad26.COV2.S versus placebo, in the PP population, including all events across age groups, with and without comorbidities. In this study, the BOD endpoint is defined as taking the value 1 for mild and moderate disease and the value 2 for severe disease (implicitly assigning a value of 0 for no disease [not infected or asymptomatic infection]). By assigning higher weight to severe infections, the BOD endpoint aims at providing higher statistical power for differentiating from placebo vaccines with increased protection against severe infections (but potentially lower VE against milder infections). The BOD evaluates the severity-adjusted VE against preventing

symptomatic incidence. The hypothesis to evaluate the VE against symptomatic infection will be based on this method. In addition, the VE against each severity category according to the case definition (severe, moderate, mild) will be summarized separately. Statistical significance for the BOD endpoint will be tested using $H_0: VE \leq 0$ at a one-sided $\alpha = 2.5\%$ according to multiplicity adjusted strategy. Details on the calculation of VE for the BOD endpoint and its associated confidence interval (for testing) and hypothesis testing will be foreseen in the SAP.

At the time of the primary analysis VE against any infection will be evaluated. At the time of the primary analysis, available N-ELISA measurements will be incorporated to evaluate VE against any infection, including asymptomatic infection. A participant will be defined as having any infection whether he/she had either a symptomatic infection (mild, moderate or severe according to the case definition) or an asymptomatic infection (as defined in Section 8.1.3.4). When all participants had 6 months of follow-up, the available N-ELISA measurements will be used to evaluate VE against asymptomatic/undetected infections only. Poisson regression will be used to estimate the VE and associated 95% confidence interval in seronegative participants in the PP analysis set for each of both analyses.

Among participants with SARS-CoV-2 infection, the effect of the study vaccine on the viral load levels at and after diagnosis as well as on the duration of SARS-CoV-2 viral load positivity will be evaluated.

The effect of the vaccine will be evaluated against molecularly confirmed COVID-19 infections requiring medical intervention once sufficient events are available. Medical interventions are evaluated as a composite endpoint of hospitalization, ICU admission, mechanical ventilation and ECMO, linked to objective measures such as decreased oxygenation, X-ray or CT findings. Poisson regression will be used to estimate the VE and the associated 95% confidence interval in seronegative participants in the PP analysis set.

All VE evaluations will be repeated regardless of their serostatus.

The statistical analysis for secondary endpoints, multiple testing strategy to evaluate the secondary objectives and the timing of the hypothesis testing will be detailed in the SAP.

See also Section 9.4.1.

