8.1.3. Efficacy Assessments

Up to Amendment 7, identification and molecular confirmation of SARS-CoV-2 infection and symptomatic COVID-19 will be performed throughout the study as described in Section 8.1.2. Up to Amendment 7, the ePRO to evaluate VE parameters will be the SIC. See Section 8.1.3.1 for Case Definition of Moderate to Severe/Critical COVID-19 and Section 8.1.3.2 for Case Definition of Mild COVID-19. Molecular confirmation of SARS-CoV-2 infection by a central laboratory will be used for the analysis of the case definition. As of Amendment 7, no identification or molecular confirmation of SARS-CoV-2 infection and symptomatic COVID-19 will be done via central testing.

COVID-19 cases will be assessed independently by a Clinical Severity Adjudication Committee (see Section 8.1.3.6). Classification of severity will be based on the highest degree of severity during the observation period (see Sections 8.1.3.1, 8.1.3.2, and 8.1.3.4) and on the Committee's clinical judgement.

Up to Amendment 7, the occurrence of COVID-19-related hospitalization and COVID-19-related complications (such as but not limited to hyperinflammatory syndrome, pneumonia, neurological or vascular complications, severe pneumonia, severe neurological or vascular events, acute respiratory distress syndrome, renal complications, sepsis, septic shock, death)⁷¹ will be monitored throughout the study.

As a secondary objective, VE in the prevention of asymptomatic SARS-CoV-2 infection and mild COVID-19 will be analyzed. For samples collected prior to implementation of Amendment 7: an immunologic test for SARS-CoV-2 seroconversion (ELISA and/or SARS-CoV-2 immunoglobulin assay) based on SARS-CoV-2 N protein, may be performed to identify cases of asymptomatic infection. This assay will be performed on samples obtained at Day 1 (before the 1st vaccination) and 14 days, 6 months, and 1 year after the second vaccination (see Section 8.1.3.5). Additionally, this assay will be performed on blood samples obtained (prior to Amendment 7) at the unblinding visit (before open-label vaccination) and at the Booster Vaccination Visit (before booster vaccination).

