8.1.3.1. Case Definition for Moderate to Severe/Critical COVID-19

For the primary -endpoint (see Section 3), all moderate and severe/critical COVID-19 cases will be considered.

Case Definition for Moderate COVID-19

- A SARS-CoV-2 positive RT-PCR or molecular test result from any available respiratory tract sample (eg, nasal swab sample, sputum sample, throat swab sample, saliva sample) or other sample

AND at any time during the course of observation^a:

Any 1 of the following new or worsening signs or symptoms:

- Respiratory rate ≥ 20 breaths/minute
- Abnormal saturation of oxygen (SpO_2) but still $>93\%$ on room air at sea level*
- Clinical or radiologic evidence of pneumonia
- Radiologic evidence of deep vein thrombosis (DVT)
- Shortness of breath or difficulty breathing

Any 2 of the following new or worsening signs or symptoms:

- Fever ($\geq 38.0^{\circ}\text{C}$ or $\geq 100.4^{\circ}\text{F}$)
- Heart rate ≥ 90 beats/minute
- Shaking chills or rigors
- Sore throat
- Cough
- Malaise as evidenced by 1 or more of the following**:
 - Loss of appetite
 - Generally unwell
 - Fatigue
 - Physical weakness
- Headache
- Muscle pain (myalgia)
- Gastrointestinal symptoms (diarrhea, vomiting, nausea, abdominal pain)**
- New or changing olfactory or taste disorders
- Red or bruised looking feet or toes

OR

* SpO_2 criteria will be adjusted according to altitude, per the investigator judgement.

** Having 2 or more elements of a symptom (eg, vomiting and diarrhea or fatigue and loss of appetite) is counted only as 1 symptom for the case definition. To meet the case definition, a participant would need to have at least 2 different symptoms.

Case Definition for Severe/Critical COVID-19

^a Participants will be asked to undertake the COVID-19 procedures until 14 days after symptom onset (COVID-19 Day 15) or until **resolution of the COVID-19 episode**, whichever comes last (see Section 8.1.2).

- A SARS-CoV-2 positive RT-PCR or molecular test result from any available respiratory tract sample (eg, nasal swab sample, sputum sample, throat swab sample, saliva sample) or other sample

AND any 1 of the following at any time during the course of observation^a:

- Clinical signs at rest indicative of severe systemic illness (respiratory rate ≥ 30 breaths/minute, heart rate ≥ 125 beats/minute, oxygen saturation (SpO_2) $\leq 93\%$ on room air at sea level*, or partial pressure of oxygen/fraction of inspired oxygen ($\text{PaO}_2/\text{FiO}_2$) < 300 mmHg)

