8.1.3.2. Case Definition for Mild COVID-19

- A SARS-CoV-2 positive RT-PCR or molecular test result from any available respiratory tract sample (eg, nasal swab sample, sputum sample, throat swab sample, saliva sample) or other sample;

AND at any time during the course of observation^a:

- One of the following symptoms: fever ($\geq 38.0^\circ\text{C}$ or $\geq 100.4^\circ\text{F}$), sore throat, malaise (loss of appetite, generally unwell, fatigue, physical weakness), headache, muscle pain (myalgia), gastrointestinal symptoms, cough, chest congestion, runny nose, wheezing, skin rash, eye irritation or discharge, chills, new or changing olfactory or taste disorders, red or bruised looking feet or toes, or shaking chills or rigors.

A case is considered mild when it meets the above case definition but not the moderate to severe/critical definition in Section 8.1.3.1.

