8.1.3.6. Clinical Severity Adjudication Committee

The Clinical Severity Adjudication Committee will be utilized for adjudication of the severity of COVID-19 cases taking into account all available relevant information at the time of adjudication. As of Amendment 7, Clinical Severity Adjudication Committee may review all cases based on available data from the passive follow-up (eg, limited to COVID-19 AE/SAE data, CIOMS forms, local laboratory results). The Clinical Severity Adjudication Committee's decisions will be considered the definitive classification of the case. The role of the Committee and adjudication process will be provided in the committee's charter and more details regarding the impact on the analysis will be provided in the SAP. The case review including severity assessments after implementation of Amendment 7 may change and will be reflected in the charter of the committee.

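### Separate VE for mild, moderate and severe cases mixes prevention with attenuation; the by-severity summary should use nested thresholds, with an unweighted VE for any symptomatic disease

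*Protocol*

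**What the plan says.** Protocol Section 9.4.2 tests symptomatic disease through a severity-weighted score: "the BOD endpoint is defined as taking the value 1 for mild and moderate disease and the value 2 for severe disease". In addition, "the VE against each severity category according to the case definition (severe, moderate, mild) will be summarized separately". No hypothesis test is attached to that second summary.

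The grading rules make the three categories exclusive:

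- Section 8.1.3.2: "A case is considered mild when it meets the above case definition but not the moderate to severe/critical definition in Section 8.1.3.1".
- Section 8.1.3: "Classification of severity will be based on the highest degree of severity during the observation period", together with the adjudication committee's judgement.
- Section 8.1.3.6: "The Clinical Severity Adjudication Committee's decisions will be considered the definitive classification of the case".

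The moderate definition in Section 8.1.3.1 does not in general exclude severe cases. For that pair, exclusivity comes from the worst-grade rule.

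Two further points bear on how the figures will be read. Section 8.1.3 makes VE against mild COVID-19 part of a secondary objective. Section 9.4.2 explains the BOD weights by reference to "vaccines with increased protection against severe infections (but potentially lower VE against milder infections".

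**The concern.** A case enters the mild-only count only if it got no worse than mild. A vaccine can lower that count by preventing disease, and can raise it by turning a would-be moderate or severe case into a mild one. One minus the rate ratio for mild-only cases nets the two effects. The same happens, more weakly, in the moderate-only row, which gains attenuated severe cases. The severe row has no grade above it and is sound.

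The mild row is the more exposed because the step from mild to moderate is short. Mild needs "One of the following symptoms: fever" or another single listed symptom, while "Any 2 of the following new or worsening signs or symptoms" already makes a case moderate. Mild cases may therefore be a small share of symptomatic disease on placebo, so a modest inflow is large in relative terms. That is an inference from the definitions; the protocol gives no share.

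What is at stake is interpretation. A reader looking for the answer to the mild-disease objective could take a low figure as failure to protect. A negative one could be read as harm, since Section 9.4.1.1 uses VE below 0% as its harm hypothesis (there for all symptomatic cases pooled and for severe cases).

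**Working it through.** **The plan's own figure.** The protocol gives no figure by severity grade. The nearest is in Section 9.2.1: 104 moderate to severe/critical events, VE 65% against a null of 30%, one-sided 2.5%, 1:1, about 90% power. In an exact binomial test on the vaccine share of events, p0 = 0.70/1.70 = 0.412 and p1 = 0.35/1.35 = 0.259. The null is rejected at 32 or fewer vaccine events of 104, and power is 89.1%. The stated figure reproduces. At VE 65% the 104 events split 77 placebo to 27 vaccine.

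**General relation.** Let m0 and m1 be the mild shares of symptomatic cases on placebo and vaccine, with equal follow-up. Then

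VE_mild = 1 − (1 − VE_sym) × (m1/m0).

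Mild-only VE lies below any-symptomatic VE whenever vaccination raises the mild share. It is negative once m1/m0 exceeds 1/(1 − VE_sym).

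**At the plan's 65%.** Hold VE against moderate to severe/critical disease at 65%. Let a fraction d of would-be moderate or severe breakthrough cases become mild, and let no mild case become asymptomatic. The fraction of symptomatic cases not prevented is 0.35/(1 − d). With r = m0/(1 − m0):

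VE_mild = 1 − [0.35/(1 − d)] × (1 + d/r), which is zero at d* = 0.65r/(0.35 + r).

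Both m0 and d are assumptions.

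| m0 | r | d* | VE any symptomatic at d* |
|---|---|---|---|
| 5% | 0.053 | 8.5% | 61.7% |
| 10% | 0.111 | 15.7% | 58.5% |
| 20% | 0.250 | 27.1% | 52.0% |
| 30% | 0.429 | 35.8% | 45.5% |
| 50% | 1.000 | 48.1% | 32.5% |

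Worked case, m0 = 10% and d = 0.2: 0.35/0.8 = 0.4375; 1 + 0.2/0.111 = 2.8; VE_mild = 1 − 1.225 = −22.5%, while VE against any symptomatic disease is 56%. At the same m0, d = 0 gives +65% and d = 0.1 gives +26%. At m0 = 50%, VE_mild is still +18% at d = 0.4.

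**All three grades, illustrative counts.** Placebo: 40 mild, 140 moderate, 20 severe. Halving every grade gives 20, 70 and 10. Move 30% of the moderate cases (21) to mild and half of the severe cases (5) to moderate. Vaccine: 41, 54 and 5.

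| Summary | Calculation | VE |
|---|---|---|
| Mild only | 1 − 41/40 | −2.5% |
| Moderate only | 1 − 54/140 | 61.4% |
| Severe | 1 − 5/20 | 75% |
| Moderate or worse | 1 − 59/160 | 63.1% |
| Any symptomatic | 1 − 100/200 | 50% |

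The moderate-only row is barely displaced from moderate or worse. The mild-only row is far from any symptomatic.

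**Sensitivity to mild cases becoming asymptomatic.** Let 30% of the 20 remaining mild cases (6) drop out of the count. The mild count is 20 − 6 + 21 = 35, so VE_mild = 1 − 35/40 = +12.5%. Any symptomatic becomes 1 − 94/200 = 53%. The sign changes, but the gap between the two figures stays.

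**The case against.** Much of the other side stands.

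- The summary is descriptive and supplementary. No type I error or power depends on it.
- The mild-only figure is not an error. It is a valid randomised comparison of how often a case peaks at mild. If attenuation leaves as many such cases as on placebo, that is a true result.
- Most nested rows already exist. Moderate or worse is the primary endpoint, severe is the same figure nested or exclusive, and VE against any infection is planned in Section 9.4.2. Symptomatic disease of all grades is tested, though through the weighted BOD score. What is not stated in the text at hand is an unweighted VE for any symptomatic disease. The objectives in Section 3 are in a part of the protocol not shown, so its absence from the whole plan cannot be confirmed.
- The illustrations rest on assumed shares and shifts. The −2.5% is 41 cases against 40, with an approximate 95% interval of −58% to +34%, and it turns to +12.5% under a plausible added shift.

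A reader might infer from this that the table will show negative efficacy against mild disease. The documents do not support that: with no attenuation, or a large mild share on placebo, the figure is clearly positive. A reader might also infer that the mild VE should be withheld. That would conflict with the secondary objective in Section 8.1.3.

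The objection does not remove the labelling problem. Presented as VE against mild disease, the figure will be read as protection, and it nets two effects.

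**Conclusion.** The point holds as an improvement to presentation and interpretation. The three categories are exclusive by the protocol's own rules. If the vaccine attenuates disease so that the mild share rises, mild-only VE understates protection against symptomatic disease and can be near zero or negative. Moderate-only VE is affected to a lesser degree.

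At 65% VE against moderate to severe/critical disease, zero is reached when about 8% to 36% of would-be moderate or severe breakthrough cases become mild. That range rests on assumed placebo mild shares of 5% to 30%, equal follow-up, and no mild case becoming asymptomatic. At a 50% mild share about 48% would have to shift. The documents give neither the mild share nor the degree of attenuation, so the sign cannot be predicted. The primary, BOD and any-infection analyses pool across grades and are unaffected.

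**What to change.** In Section 9.4.2, present the by-severity summary on nested thresholds: severe/critical; moderate or worse (already the primary endpoint); and any symptomatic disease, unweighted, beside the BOD result. Mild-only and moderate-only VE may be kept for the objective in Section 8.1.3. Label them as the incidence of cases whose worst grade was mild or moderate, and state that they do not measure protection against disease of at least that grade.

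The cost is one extra row and a footnote. The case definitions, data collection and testing strategy stay as they are.

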9.2. Sample Size Determination

9.2.1. Efficacy (Total Sample Size)

For the double-blind phase, the sample size is determined using the following assumptions:

- a VE for molecularly confirmed, moderate to severe/critical SARS-CoV-2 infection of 65%.
- type 1 error rate $\alpha = 2.5\%$ to evaluate VE of the vaccine regimen.
- a randomization ratio of 1:1 for active versus placebo

Events are defined as first occurrence of molecularly confirmed, moderate to severe/critical COVID-19 according to the case definition in Section 8.1.3.1 in the PP population at least 14 days after the second vaccination with study vaccine (Day 71).

Under the assumptions above, a total of 104 events will provide approximately 90% power to reject the null hypothesis of $H_0: VE \leq 30\%$, according to the primary endpoint case definition of moderate to severe/critical COVID-19 (Section 8.1.3.1).

If the primary hypothesis testing is successful, secondary objectives will be evaluated against a null hypothesis employing a lower limit $VE > 0\%$. The method to perform hypothesis testing of primary and secondary objectives preserving the FWER will be specified in the SAP. The FWER will be controlled at 2.5%.

Sample Size Justification

Based on the variations in seroprevalence, degree of social distancing and use of personal protective equipment, it is not feasible to estimate the incidence rates that can be attained at the time of the start of this study. It is also unknown which local regulations (eg, potential lockdowns) will be in effect at that time.

The sample size is approximately 15,000/group (approximately 30,000 in total) and is determined based on estimated annualized incidence rate of moderate to severe/critical COVID-19 of 1% to 4% at the start of the study.

Assuming 2 months of recruitment and 10% seroprevalence, the selected sample size will have a high probability (approximately 90%) to have reached an efficacy signal within 15 months after first participant vaccinated for an assumed $VE \geq 65\%$ under an assumed incidence of 1.4% in Month 1-3, and waning of incidence thereafter, eg, 50% reduction at Month 4 (0.70% annualized) followed by further reduction to 0.58%.

With higher incidences at the start of the study, the timelines to efficacy will shorten.

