9.4.1. Primary Endpoint Evaluation for the Double-blind Phase

The double-blind phase of the study is designed to test the primary hypothesis of VE in the PP population: H0: VE $\leq 30\%$ versus H1: VE $> 30\%$ and will be evaluated at a 2.5% 1-sided significance level.

The primary endpoint will evaluate the first occurrence of molecularly confirmed, moderate to severe/critical COVID-19 according to the case definition in Section 8.1.3.1, with onset at least 14 days after the second vaccination (Day 71) with Ad26.COV2.S versus placebo, in the PP population, including all events from both age groups, with and without comorbidities.

Participants included in the seronegative analysis set are those participants with a negative SARS-CoV-2 serology test result at baseline.

The unblinding visit marks for a participant the end of the double-blind phase, and the start of the open-label phase. For a given participant, all data up to the unblinding visit will be incorporated in the analysis of the double-blind phase.

The minimum criteria that may trigger the primary analysis before at least 90% of participants are unblinded is if the prespecified harm boundaries have been crossed.

A successful primary efficacy conclusion will require establishing the hypothesis H1: VE $> 30\%$ for the primary endpoint.

Exact Poisson regression will be used to estimate the VE and associated CI taking into account the follow-up time. To evaluate the primary null hypothesis: H0: VE $\leq 30\%$ versus H1: VE $> 30\%$ for the primary endpoint, 95% 2-sided confidence interval based on Poisson regression model will be used.

The decision rules for harm are detailed in Section 9.4.1.1.

For any case definition to be considered for classification of COVID-19 cases, there needs to be at least one SARS-CoV-2 positive RT-PCR or molecular test result from any available respiratory tract sample (eg, nasal swab sample, sputum sample, throat swab sample, saliva sample) that is confirmed by the central laboratory. It is possible that not all samples can be confirmed at the time of the analysis. Hence, a sensitivity analysis may be performed using all RT-PCR or molecular test result, regardless of the confirmation by the central laboratory.

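### The viral-load and duration comparison is made only among infected participants, a group the vaccine helps select, so it should be reported as descriptive with a selection range and not as a vaccine effect

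*Protocol*

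**What the plan says.** Protocol section 9.4.2 sets the analysis set and the target in one sentence: "Among participants with SARS-CoV-2 infection, the effect of the study vaccine on the viral load levels at and after diagnosis", continuing "as well as on the duration of SARS-CoV-2 viral load positivity will be evaluated". It names no model, test or success criterion for viral load. It leaves the statistical analysis and the multiple-testing strategy for secondary endpoints to the SAP, which was not among the documents reviewed.

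The paragraph just before it treats infection as something the vaccine may prevent: "At the time of the primary analysis VE against any infection will be evaluated". That endpoint counts symptomatic infections of any severity and asymptomatic ones, including those shown only by N-serology.

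Sections 8.1.1 and 8.1.2.2 say when swabs are taken. Follow-up of an episode starts from qualifying symptoms or a positive RT-PCR obtained outside the study. The alternate-day sampling continues for participants who still meet the symptom criteria at Day 3-5 or have a positive early swab. Under section 8.1.3.4 an infection can also be counted on serology alone.

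**The concern.** Randomisation makes the two arms comparable. It does not make the infected members of the two arms comparable once the vaccine changes who is infected. The infected placebo recipients are a mixture of people who would have been infected either way and people whom the vaccine would have protected. The infected vaccinees, if the vaccine never causes infection, are only the first kind. If these two kinds of people would carry different viral loads, the arms differ even when the vaccine alters no individual's load.

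The protocol gives a reason to take this seriously. Its rationale for the burden-of-disease (BOD) endpoint in section 9.4.2 allows for stronger protection against severe than against milder infection. If viral load tracks severity (an assumption), protection would then depend on load.

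Triggered swabbing adds a second layer. If vaccination makes infections milder, it also changes which infections are sampled.

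What is at stake is a secondary conclusion. The report could say that vaccination lowers, or raises, viral load in breakthrough infection when the data show only which infections remained to be measured.

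**Working it through.** **1. The plan's own figure.** The protocol gives no figure for viral load, so the check starts from the event count, which uses the same assumed efficacy. Inputs from sections 9.2.1 and 9.4.1: efficacy 65%, null 30%, one-sided 2.5%, and "a randomization ratio of 1:1 for active versus placebo". Given 104 events, the number in the vaccine arm is binomial.

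- Share under the null: 0.70/1.70 = 0.412. Share under the alternative: 0.35/1.35 = 0.259.
- Reject at 32 or fewer vaccine events: exact one-sided alpha 0.0187, power 89.1%.

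This agrees with the statement that "a total of 104 events will provide approximately 90% power". The expected split is 104 × 0.259 = 27 vaccine and 77 placebo events.

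**2. Which efficacy applies.** The 65% is "a VE for molecularly confirmed, moderate to severe/critical SARS-CoV-2 infection of 65" per cent, that is, for the primary case definition. The viral-load set is everyone infected, and no efficacy is assumed for that group. A range of 30% (the primary null) to 65% is used below as an assumption.

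**3. Two-group identity.** Let A be people infected under either arm and P those infected only under placebo, with mean log10 loads m_A and m_P. Assume that the vaccine never causes infection and has no effect on any individual's load.

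- Infected placebo mean: (1 − VE) m_A + VE m_P. Infected vaccine mean: m_A.
- Vaccine minus placebo = −VE × (m_P − m_A).

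With an assumed gap of 0.5 to 1.0 log10 in either direction, the size runs from 0.30 × 0.5 = 0.15 to 0.65 × 1.0 = 0.65 log10. With no gap it is zero.

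**4. Graded selection.** Let x be the standardised load a person would have had on placebo, taken as normal. Let the chance of still being infected under vaccine be 1/(1 + exp(−(a + s·x))), with a chosen so that the average is 1 − VE. The shift in SD units is the mean of x times that chance, divided by (1 − VE). The last column is the limiting case in which exactly the lowest loads are prevented, φ(z)/(1 − VE) with z the VE quantile.

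| VE | slope 0.5 | slope 1 | slope 2 | limit |
|---|---|---|---|---|
| 30% | 0.14 SD | 0.25 SD | 0.37 SD | 0.50 SD |
| 65% | 0.31 SD | 0.54 SD | 0.80 SD | 1.06 SD |

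At an assumed SD of 1.5 log10, the slope columns run from 0.14 × 1.5 = 0.2 to 0.80 × 1.5 = 1.2 log10. A slope of zero gives no shift, and negative slopes give the mirror image.

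**5. Check of sign by simulation.** In 4,000,000 simulated people with no individual effect on load, the vaccine-minus-placebo difference among the infected was:

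- +0.38 log10 when low-load infections were preferentially prevented (VE 55%);
- 0.00 when prevention was unrelated to load (VE 65%);
- −0.50 when high-load infections were preferentially prevented (VE 71%).

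**6. What a test would do.** As an illustration, take 27 v 77 infected, borrowed from step 1; the actual number infected is not given. The standard error is SD × √(1/27 + 1/77), which is 0.335 at SD 1.5. A nominal two-sided 5% test would then reject, with no individual effect:

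| spurious difference | SD 1.0 | SD 1.5 | SD 2.0 |
|---|---|---|---|
| 0.33 log10 | 31% | 16% | 11% |
| 0.65 log10 | 83% | 49% | 31% |

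Steps 3 to 6 cover selection by prevention only. The further effect of triggered swabbing is not quantified.

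**The case against.** The best defence is that viral load in breakthrough cases is a legitimate question in its own right. Section 9 describes itself as a general description, and the SAP may already contain sensitivity analyses and cautions. The protocol says only that the effect will be evaluated and ties no hypothesis to it. All of that is fair, and the absence of a model or sensitivity analysis from the protocol is not the finding. What stands is that the protocol itself fixes both the infected-only set and the description of the contrast as an effect of the vaccine.

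Four stronger readings are tempting and are not supported.

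- **About two thirds of infections are missing from the vaccine arm.** The 65% belongs to moderate to severe/critical disease. Efficacy against any infection is not stated.
- **The bias reaches 1.6 log10.** That is the limiting case, 1.06 × 1.5, in which exactly the lowest 65% of loads are prevented. The strongest graded selection considered gives 1.2.
- **The comparison is known to be biased in a given direction.** The direction, the selection strength and the SD are all assumed here.
- **A zero-scored composite should replace the infected-only comparison.** It answers a different question and is driven partly by efficacy against infection. Infections found only by serology may also have no swab, so they cannot simply enter it.

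**Conclusion.** The concern holds as one of interpretation. As written, section 9.4.2 attaches a vaccine effect to a contrast that randomisation does not protect, and that contrast can differ from zero in either direction with no individual effect on viral load.

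As an illustration only, the spurious shift is about 0.14 to 0.80 SD, or 0.2 to 1.2 log10. This rests on an efficacy against infection of 30% to 65%, logistic slopes of 0.5 to 2, normally distributed loads and an SD of 1.5 log10, none of which the documents give for this group. The same reasoning applies to duration of positivity, for which no size was computed. The primary endpoint, sample size and type I error control for the primary test are untouched. The change is worth making because it alters what may be concluded from a stated secondary analysis.

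**What to change.** 1. Keep the infected-only comparison of viral load and duration. State in section 9.4.2 and in the SAP that it is descriptive and is not a randomised vaccine effect.
2. Give it a principal-stratum sensitivity range for the always-infected. One way, assuming that the vaccine never causes infection, is to compare infected vaccinees with the highest and then the lowest (1 − VE) share of placebo loads, using efficacy estimated for the infections that were actually sampled.
3. Add a supportive analysis of all per-protocol participants by assigned arm, using a viral-load burden score (peak or area under log load, 0 if not infected). This follows the BOD endpoint, which already gives 0 to participants without disease. Treat infections found only by serology as missing viral load and not as 0, and say how the missing values are handled.

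The cost is some wording and one extra analysis, with no new visits or samples. The downside is that the composite partly reflects efficacy against infection, which is why it is supportive and not a replacement.
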